Missing values. We will use an intent-to-treat analysis treating missing values for breastfeeding (BF) status as non-BF status. In addition, the mixed effect models will provide valid estimates of efficacy if the proportion of missing values is less than 10%.¹

Interim analyses. Three interim analyses will be conducted to formally monitor the accumulating data in the study, at 2 months, 4 months, and 6 months, with expected increase of BF rate by 25% as a significant increase at 6-month postpartum. With the overall proposed recruitment number of 168 participants, the α -levels are 0.012, 0.016, and 0.022 for 2-month, 4-month, and 6-month postpartum, based on the standardized Z-values for the two groups from the O'Brien-Fleming function with cumulative $\alpha=0.05$ with power of 85%. If we do not see significant increases (at pre-required α -level) either at 2 or 4 months, we will increase the number of participants to recruit to sustain the power.

Logistic regression will be used to compare groups on the primary binary outcomes of point-prevalence of BF status at 1-, 3-, 6-, and 12-month postpartum; survival analyses will also be used to assess continuation. The models will include terms for study group, time, and the group by time interaction. Although propensity score-matched randomization will minimize the need for covariate adjustment, theoretically important covariates and differences will be considered for inclusion in adjusted analyses to improve their precision. Since the 12-month postpartum BF rate is an exploratory outcome, we will use a conservative significance level of .001 versus .05 for BF rates at other time points to decrease the possibility of having a false-positive statistical outcome. The Cochran-Armitage Trend Test will also be used to examine the trend of BF from 1-month through 6-month postpartum and from 1-month through 12-month postpartum. These analyses will also be used to examine the impact of *SC+BF1* on exclusive BF rates at each time point.

References

1. Bennett DA. How can I deal with missing data in my study? *Australian and New Zealand journal of public health*. 2001;25(5):464-469.

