9.2 Inclusion and Exclusion Criteria

To be eligible for the study, mothers must: (1) initiate BF; (2) be WIC-enrolled or eligible to enroll in WIC services; (3) reside and plan to stay in the study county for 12 months postpartum; (4) consent voluntarily; (5) understand 5th grade level of English; and (6) be 18 years or older. We will exclude mothers whose babies are medically contraindicated against BF, who are hospitalized for severe postpartum medical issues, who have ongoing illicit drug use issues, who had a psychiatric hospitalization within the last three months, who currently have suicidal thoughts or attempts. For women who are incarcerated during 6 months of study participation as well as participants who fail to attend scheduled visits during 6 months of study participation for more than 3 months, their study participation will be terminated.

We include infants of the participants, but infants are not subject to inclusion criteria. Written permission for a minor by a parent or legal guardian will be required for infant participants.

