9.5 Study Endpoints

The primary outcome is the BF continuation rate at 6-month postpartum. This is determined by observed breastfeeding which includes: audible swallowing, regular suck/swallow/breath patters, visible milk in the infant's mouth after the infant is not latched anymore. Or, in the case of pumping moms, pumped milk and successful feeding to the infant. We hypothesize that the isolated effect of monthly incentives contingent on BF in SC+BFI will increase BF rates by 25% at 6-month compared to SC.

The exploratory outcome is the BF continuation rate at 12-month postpartum. We will hypothesize that SC+BFI will increase the BF rate at 12-month, compared to SC.

10.0 Study Procedures Involved:

- 10.1 We will use a randomized, two-group design (Standard Care+Breastfeeding Support vs. Standard Care+Breastfeeding Incentives).
- 10.2 We will use a permuted block random assignment (with block size = 6), assigning participants to one of 2 groups: *Standard Care* or *Standard Care + BFI*. This will allow us to keep group sizes approximately equivalent during the study maintaining an approximately equal size for the 2 groups. We will use propensity score matching to randomize the participants based on study site, as well as Black race and Puerto Rican ethnicity to maximize internal validity.

Allocation to study groups in randomization will be administered by [name] (Co-I) who will not have access to collected data until the end of the study. [name] will generate computer-

generated random numbers and keeps the original sequence in a password-protected electronic file that no other research staff can access. [name] will program the list of random numbers into an electronic file on RedCap which will automatically assign each participant to either condition. Other research staff can only view the result of randomization so that the allocation process remains concealed.

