- 10.4 Assessment.** All participants in both groups will be asked to complete periodic assessments at 1-, 3-, 6-, 9-, and 12-month postpartum intervals either at home or by phone. Assessments at 1, 3, and 6-month postpartum will be conducted by phone one week prior to home visit appointments and those at 9 and 12-month postpartum will be conducted in person. An RA will call a participant and make an appointment a week prior to the scheduled assessment date. The pilot study had the 97% follow-up rate at 6-month postpartum with this approach. Research measures for each timepoint is shown below. When a participant stops BF, she will be asked to explain the psychosocial or medical reasons of stopping BF, such as return to work, workplace policy on pumping, and lack of social support. Appointment cards will be given to participants for future appointments.
- 10.5 Payments.** Participants in *SC+BFI* will receive dollar amount incentives on a pre-paid credit card for breastfeeding. This type of system functions just like a Master Card and allows remote reloading. This system has been feasibly and effectively used by clinical populations. Un-blinded Project Coordinator will credit a dollar amount remotely on a Master Card for each participant. Participants in *SC* will receive a lump sum payment in form of retail gift cards at the end of 6 months based on the number of completed home visitations. The lump sum will be calculated after 6th month home visitation, and unblinded staff will notify the participant that the payment is ready for pick-up at the Temple University College of Public Health. All participants will receive retail gift cards for completing periodic assessments. Gift cards will be delivered in person on the day of in-person assessments, and at the next home visitation for phone-based assessments that are completed prior to the upcoming home visitation appointment. All participants will receive a gift basket at the 12-month visit as well.
- 10.6** Data source includes validated instruments for interview questions, breastfeeding observation records, and biological data and samples.

10.7 Description of data to be collected at each timepoint.

Screening/First home visitation:

Questionnaires to complete with staff between now and at the first home-based research assessment include:

Questionnaires	Description	When administered
Locator form	Participant contact information and emergency contacts	At the hospital floor

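### Missed visits coded as non-BF, with no survival event or gap rule defined, can record weaning in mothers later seen breastfeeding and distort the continuation effect in either direction

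*Combined protocol and SAP*

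**What the plan says.** Under Statistical Design and Power, the Missing values paragraph sets out an intent-to-treat analysis "treating missing values for breastfeeding (BF) status as non-BF status". No exception is given for a gap that ends with an observed feed. The next sentence says that "the mixed effect models will provide valid estimates of efficacy if the proportion of missing values is less than 10" percent; that does not define a survival event either.

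The analysis paragraph that follows plans logistic regression of "point-prevalence of BF status at 1-, 3-, 6-, and 12-month postpartum" and adds that "survival analyses will also be used to assess continuation". It states no event, event date, censoring rule or visit grid for the survival analysis. It does not say whether the imputed status feeds that analysis.

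Section 9.5 is explicit about the primary: "The primary outcome is the BF continuation rate at 6-month postpartum", determined by observed breastfeeding.

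Four other parts of the protocol bear on missed visits:
- Section 10.3 sets monthly home visits with BF observation, a one-week make-up window, and an unannounced home visit after three failed phone attempts.
- Section 9.2 ends participation for "participants who fail to attend scheduled visits during 6 months of study participation for more than 3 months", so shorter gaps stay in the data. Under section 12.1, terminated mothers are not followed further.
- Section 10.4 provides for an interview on weaning: "When a participant stops BF, she will be asked to explain the psychosocial or medical reasons of stopping BF". Section 10.7 collects a daily infant-feeding log at the monthly visits and at months 9 and 12.
- Sections 10.2 and 10.3 pay SC+BFI mothers at a visit only if BF is demonstrated. SC mothers are paid a lump sum after month 6 according to completed visits.

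**The concern.** Take a mother who misses month 2, is not reached by the make-up or unannounced visit, and is observed breastfeeding at months 3 to 6. At month 6 she counts as BF. If the missing-value rule also supplies her status for the survival analysis, her first non-BF record is month 2 and she is weaned there, although the trial itself later sees her feeding. A mother missed at month 3 and seen feeding at month 6 likewise counts as non-BF in the 3-month rate.

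Missing-as-failure is usually defended as conservative when nothing further is known. That defence does not cover a gap closed by a later observation. Nor is the rule conservative for a comparison between arms when the arms miss visits at different rates. The incentive for attending a visit differs by arm, so equal rates cannot be taken for granted. At stake are the estimated continuation effect, its power and its type I error, together with the 1- and 3-month rates.

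**Working it through.** **Inputs.** From the documents: 168 mothers, 1:1, so 84 per arm; an increase of 25, read as percentage points; monthly visits to month 6. The control rate is not a stated design value. I use 20%, which section 5.1 gives for Medicaid-eligible mothers in Delaware, hence 20% vs 45%. Further assumptions: miss rate m per visit, independent across visits and of BF status; constant weaning hazard; two-sided 0.05 for the log-rank test.

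**The plan's own figure.** The SAP gives no number for the survival analysis, but 168 can be recovered. With 20% vs 45%, two-sided alpha 0.022 and 85% power:
- n = [2.290·√(2·0.325·0.675) + 1.036·√(0.20·0.80 + 0.45·0.55)]² / 0.25² = 76 per arm (N = 152).
- The continuity correction raises this to 84 per arm (N = 168).

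So 20% vs 45% is a reasonable base case. The 168 is not in dispute here.

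**False weaning, equal misses.** Among mothers observed breastfeeding at month 6, the share with at least one earlier missed visit is 1 − (1 − m)⁵: 14%, 23% and 41% for m = 3%, 5% and 10%. Literal coding records all of them as weaned.

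**Survival estimate at month 6.** A mother survives only if she is still breastfeeding and attends all six visits, so the estimate is S(6)·(1 − m)⁶.
- m = 3%: 37.5% − 16.7% = 20.8 points
- m = 5%: 33.1% − 14.7% = 18.4 points
- m = 10%: 23.9% − 10.6% = 13.3 points

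**Log-rank power, simulated at 84 per arm.** Literal coding gives about 92%, 86–88% and 75–78% (ranges are simulation error). If a gap before later observed BF counts as BF, power is about 95–96% in all three cases.

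**Direction when the arms differ.** The true hazard ratio is ln(0.45)/ln(0.20) = 0.496. Simulated hazard ratios under literal coding, monthly grid:

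| Misses per visit, SC / SC+BFI | HR |
|---|---|
| 3% / 3% | 0.55 |
| 5% / 5% | 0.58 |
| 10% / 10% | 0.64 |
| 5% / 10% | 0.75 |
| 10% / 5% | 0.50 |
| 15% / 5% | 0.43 |
| 10% / 2% | 0.41 |
| 5% / 0% | 0.42 |

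The effect shrinks in the first four rows, is unchanged in the fifth and is inflated in the last three. On a 1/3/6-month grid the pattern is the same but weaker: 0.55 at 5%/5%, 0.65 at 5%/10% and 0.45 at 15%/5%. With the gap rule, the monthly-grid HR is 0.50 to 0.51 for equal misses of 3% to 10%. It is 0.48 at 10%/2%, so the rule removes most of the distortion but not all.

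**Type I error.** With 30% BF at 6 months in both arms, literal coding rejects in about 20–23% of trials at 10% vs 5% misses, and in 46–49% at 10% vs 2%. With the gap rule it is 5–6%.

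**6-month primary.** Only the month-6 visit matters. Equal 5% misses give 0.95 × 25 = 23.8 points. SC 15% and SC+BFI 5% give 0.95 × 45 − 0.85 × 20 = 42.75 − 17.0 = 25.8 points.

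**3-month rate.** Under constant hazard the true rates are √0.20 = 44.7% and √0.45 = 67.1%, a 22.4-point difference. Equal 5% misses give 0.95 × 22.4 = 21.3 points. This shift is small because only one visit is involved, whereas the survival analysis accumulates errors over six.

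**The case against.** The strongest objection is that the SAP never says the imputed status defines the survival event. Weaning could be dated from the feeding logs and the stop-BF interview, and the pilot reported duration in days. This stands: the false events follow from a literal reading, not from a stated instruction. But the missing-value rule is the only one in the SAP that assigns a BF status to a missed visit, and nothing tells the analyst to use the logs instead.

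A second objection concerns size. The make-up week and unannounced visit will limit gaps, and 97% of pilot mothers completed all postpartum assessments, the one loss being a move out of state. Independent misses of 3%, 5% and 10% imply that only 83%, 74% and 53% attend all six visits, so 10% is a stress case. That is fair, although pilot attendance at monthly visits is not reported. At 3% and 5%, literal-coding power still exceeds the planned 85%.

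A third is that misses may not be independent of BF status. An SC+BFI mother who has weaned has less reason to attend, so some missed visits will be true non-BF. This also stands. It leaves untouched the mothers later observed feeding, whose code is wrong whatever the cause of the gap.

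A reader might infer that the rule always understates the benefit. The documents do not support that. The only by-arm evidence is the pilot, where the single loss was in the control arm (17/18 vs 18/18 completing). One mother settles neither equality nor direction.

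**Conclusion.** The concern holds as a gap in the SAP with a quantifiable consequence. The missing-value rule has no exception and the survival event is undefined. Applied literally, the two together record weaning before observed breastfeeding. The 1- and 3-month rates can carry the same false non-BF codes, with a smaller effect.

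The consequence is distortion whose direction depends on missingness by arm: attenuation and lost power with equal misses, or with more in SC+BFI; inflation and false positives if SC misses enough more. The sizes depend on the assumed miss rates, constant hazard, independence of misses from BF status, and 20% vs 45% at 6 months. The need for a rule does not depend on them.

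A reader might also infer that the coding contradicts or undermines the primary outcome. It does not: 6-month point prevalence makes no use of earlier missed visits and moves by about a point in the cases shown, provided month 6 is estimated as its own time point. The disagreement is confined to the supplementary survival analysis, for mothers with an earlier gap who are observed feeding at month 6.

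**What to change.** Amend the SAP as follows, before any comparison by arm.

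1. For the survival analysis and the 1- and 3-month rates, count a missed visit followed by a later observed BF as BF.
2. Define weaning as occurring between the last visit with observed BF and the first attended visit after it without BF and with no later observed BF. Date it from the feeding log and stop-BF interview where available. State the visit grid.
3. For permanent loss, state one rule: an event just after the last observed BF, in line with the intent-to-treat rule, with censoring at that point as a sensitivity analysis.
4. Say explicitly that the missing-as-non-BF rule continues to apply to the 6-month primary.
5. Report missed visits by arm and month, so that readers can judge the distortion that remains.

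The cost is SAP wording and a few lines of code; no new data are needed. The small downside is that a mother who stopped and restarted within a gap is counted as continuing.

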- 3.1 We propose to examine the efficacy of monthly financial incentives contingent on observed breastfeeding (BF), supplemental to existing support from the Special Supplemental Nutrition Program for Women, Infants, and Children (WIC) program and home-based individual BF support, among low-income mothers. Low-income racial/ethnic-minority women breastfeed for an average duration of four months despite evidence-based recommendations by the American Academy of Pediatrics to exclusively breastfeed for six months of life in addition to continued breastfeeding through the first year. Insufficient duration of any BF is related to multiple maternal and child health problems, and increases in BF duration could be cost saving medically and societally. Though peer support has been effective in prolonging BF duration, the effect has not been as strong for WIC-eligible, low-income mothers. An incentive-based intervention was tested among low-income Puerto Rican mothers in a pilot study (R03HD077057) resulting in promising outcomes of monthly financial incentives contingent on observed BF for 6 months combined with WIC BF usual care, compared to WIC BF usual care only (BF rates: 89% vs. 44% at 1-month; $p = 0.01$; 89% vs. 17% at 3-month; $p < 0.01$; 72% vs. 0% at 6-month; $p < 0.01$; $N = 36$). We propose a 2-group parallel randomized controlled trial in which half of the 168 WIC-eligible mothers recruited to the trial will be allocated into each of the two study groups: (1) Standard Care BF Support (**WIC support + home-based individual support; Standard Care (SC)**) and (2) Incentives contingent on demonstrating successful BF (**SC + Breastfeeding Incentives; SC+BFI**). Participants randomized into SC will receive standard breastfeeding services from WIC and home visitations for individual support and problem-solving. Participants randomized into SC+BFI will receive the same services as Control except that monthly financial incentives are contingent on observed BF and delivered at the end of each month. The study will be conducted in two regional sites with high concentrations of low-income racial/ethnic minority mothers, Philadelphia, PA and Newark, DE. The primary outcome will be the BF rate for 6-month postpartum, the exploratory outcome will be the BF rate at 12-month postpartum, and the secondary outcomes will be infant outcomes (i.e., weight gain and emergency room visits). We hypothesize that SC+BFI will increase the BF rate by 25% at 6-month postpartum and have significantly lower infant weight gain and incidents of ER visits for infants at 3-month postpartum, compared to SC. We will track the costs of intervention, formula purchased by mothers, and infant medical care in both groups. We will also conduct interviews with corporate representatives and insurance companies to explore community- and policy-level support to

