Home-based support and problem-solving component: Blinded RA will also provide individual support and problem-solving in addition to WIC services. At each monthly home visit, blinded RA will ask participants to demonstrate BF, praise participants' efforts to continue BF, problem-solve issues around BF, provide local BF resources, and identify any issues with BF and other medical and psychosocial needs. Signs to verify ongoing BF include audible swallowing of breastmilk, regular suck/swallow/breathing patterns, visible milk in an infant's mouth, and (in case of pumping moms) pumped milk and successful feeding of an infant. When a participant has trouble with BF, she will be referred to a certified lactation consultant (CLC). Should a participant report any adverse maternal and infant outcome during the study period, blinded RA will document the event, report to the PI and IRBs, and make referrals as needed. Participants in SC will be asked to monitor their nutritional habit each month and to complete 24-hour recalls for each month. Research staff will mark a tally on a checklist at each monthly visit, and completion of nutritional monitoring will lead to a lump sum compensation for a total potential earning of \$240 with \$40 per completed monthly nutritional monitoring. Participants will also receive diapers and wipes at every home visit. This is comparable to the SC+BFI group to control for the incentive amount. However, in SC, this payment is tied to monitoring the nutritional habit and paid in a lump sum— not to observed BF at each month as in the SC+BFI group.

If a participant misses an appointment, this will be counted as incompliance with monthly nutritional monitoring. The participant will be given an opportunity to make up for the missed appointment within one-week timeframe from a due date. Blinded RA will contact a participant a week prior to the due date and make an appointment. After 3 attempts to reach a participant by

phone, blinded RA will provide a daytime unannounced home visit. Participants will be informed of potential unannounced home visits during study consent.

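### The Cochran-Armitage trend test is planned across repeated visits of the same mothers, so its standard error is wrong, in a direction the plan does not fix

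*Combined protocol and SAP*

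**What the plan says.** The Data Analyses text under Statistical Design and Power specifies the trend test in one sentence: "The Cochran-Armitage Trend Test will also be used to examine the trend of BF from 1-month through 6-month postpartum" "and from 1-month through 12-month postpartum". It does not give the visits, the scores, the significance level or the handling of repeated observations on one mother.

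Two parts of the protocol bear on which visits could enter:

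- Section 10.4 (Assessment): "All participants in both groups will be asked to complete periodic assessments at 1-, 3-, 6-, 9-, and 12-month postpartum intervals".
- Section 10.3 (home-based support component): "At each monthly home visit, blinded RA will ask participants to demonstrate BF".

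The paragraph containing the trend test sets the logistic regression on "point-prevalence of BF status at 1-, 3-, 6-, and 12-month postpartum" and adds that "survival analyses will also be used to assess continuation". It ends by extending these analyses to "exclusive BF rates at each time point". The missing-values paragraph counts a missing breastfeeding status as not breastfeeding, so every mother supplies a value at every visit. Mixed effect models are mentioned only in that paragraph and are not linked to the trend test.

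**The concern.** Cochran-Armitage takes its variance from independent binomial counts at each level. When the levels are visits and each mother contributes to all of them, the counts are correlated and that variance is wrong.

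Positive correlation between distant visits makes the true variance of a trend smaller than the test assumes, so the test is conservative. Correlation that is strong between neighbouring visits but fades over the window can make the true variance larger, so the test is liberal.

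A modest decline in breastfeeding could therefore be missed, or a trend declared slightly too often. A reader of the results could not tell which error applied. The same holds for exclusive breastfeeding.

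**Working it through.** The plan gives no figure for this test, so there is none to reproduce.

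**Inputs from the documents.** There are 168 mothers in two equal groups, so 168/2 = 84 per arm. Pilot rates at months 1, 3 and 6 are 44/17/0% (control) and 89/89/72% (incentive), from sections 3.1 and 4.1.

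**Assumptions.** The test is run within an arm at two-sided 5%, with visit month as the score. The within-mother correlation is not given, so a range is used.

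**Formula.** Let c be the centred visit months, p̄ the mean rate and V the within-mother covariance of breastfeeding status. Then

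ratio = Cochran-Armitage SE / true SE = √[p̄(1−p̄)·Σc²] / √(c′Vc).

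A ratio above 1 means the test is conservative. With no trend, the real level is 2·[1 − Φ(1.96 × ratio)].

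**Case 1: stopping is permanent.** Here V_ij = min(p_i, p_j) − p_i·p_j. For visits 1, 3 and 6, c = (−7/3, −1/3, 8/3) and Σc² = 114/9 = 12.67.

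Worked example, pilot incentive rates: p̄ = 0.833, so the numerator is 0.1389 × 12.67 = 1.759. The covariances give c′Vc = (64/9) × (0.0979 − 2 × 0.0792 + 0.2016) = 1.003. The ratio is √(1.759/1.003) = 1.32.

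| Rates at months 1/3/6 | Ratio, visits 1, 3, 6 | Ratio, six monthly visits (rates interpolated) |
|---|---|---|
| 44/17/0% (pilot control) | 1.17 | 0.91 |
| 89/89/72% (pilot incentive) | 1.32 | 1.10 |
| 60/40/20% (assumed) | 1.42 | 1.15 |
| 80/65/45% (assumed) | 1.42 | 1.17 |
| 80/70/60% (assumed) | 1.63 | 1.35 |
| 80/77/70% (assumed) | 1.98 | 1.64 |

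**Case 2: flat rate, AR(1) correlation of breastfeeding status per month.** Each cell gives the ratio and the real level at nominal 5%.

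| Visits | 0.3 | 0.5 | 0.7 |
|---|---|---|---|
| 1, 3, 6 | 1.00 (5.1%) | 1.01 (4.8%) | 1.09 (3.3%) |
| 1 to 6 monthly | 0.88 (8.4%) | 0.85 (9.6%) | 0.90 (7.9%) |
| 1, 3, 6, 12 | 0.99 (5.3%) | 0.96 (5.9%) | 0.95 (6.3%) |
| 1, 3, 6, 9, 12 | 0.98 (5.6%) | 0.93 (6.8%) | 0.89 (8.2%) |
| 1 to 6, 9, 12 | 0.92 (7.3%) | 0.85 (9.7%) | 0.79 (11.9%) |

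At six monthly visits the inflation has gone by a correlation of 0.8 (ratio 0.995, level 5.1%). At 0.95 all five visit sets are conservative.

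**Simulated level, no trend.** This used 84 mothers, 20,000 replicates and breastfeeding rates of 20, 40 and 70%. The correlation here is on a latent scale, so these rates are not directly comparable with Case 2.

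- Visits 1, 3, 6 with exchangeable correlation 0.3 to 0.8: Cochran-Armitage rejects in 0.2 to 3.3%.
- Six monthly visits with AR(1) 0.3 to 0.7: it rejects in 6.6 to 8.4%.
- A linear contrast computed per mother rejects in 4.7 to 5.2% in the same cells.
- With independent observations, Cochran-Armitage rejects in 4.9 to 5.2%, as it should.

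**Simulated power, visits 1, 3, 6, permanent stopping, 84 mothers.**

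| Rates | Cochran-Armitage | Mother-level contrast |
|---|---|---|
| 80/77/70% | 21% | 97% |
| 80/75/65% | 68% | over 99% |
| 80/70/60% | 93% | 100% |
| 89/89/72% | 95% | 100% |
| 44/17/0% | 100% | 100% |

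As a lower bound that does not use the contrast, an exact sign test of month 1 against month 6 needs at least 6 stops (p = 0.031). Its power is 86% for a fall from 80 to 70% and 99% for a fall from 80 to 65%.

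A GEE logistic model with clustered standard errors (600 replicates) rejected in 4.7% and 5.7% of runs in two no-trend settings. Its power was 97% at 80/77/70%.

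**The case against.** **The visits can be inferred.** The same paragraph lists months 1, 3, 6 and 12 for breastfeeding status. On that reading the 1-to-6-month test is close to nominal or conservative in every case tried, and the 12-month window reaches at most 6.3% over correlations of 0.3 to 0.7. The larger inflation needs monthly visits taken from the home-visit procedure. This is a fair reading, but the trend sentence does not say it, and an SE that is too large is still an error.

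**The liberal cases imply frequent restarting.** At a 40% rate, AR(1) of 0.3 to 0.7 means that 0.4 × 0.7 = 28% down to 0.4 × 0.3 = 12% of non-breastfeeding mothers resume each month. That is hard to square with a plan that analyses stopping as an event, although counting a missed visit as not breastfeeding can create apparent restarts. The liberal direction should be held more loosely than the conservative one.

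**The striking power loss uses assumed rates.** This stands: 80/77/70% is not in the documents, and at the pilot rates power is 95% or more.

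**A valid layout may be intended.** Comparing arms across ordered months of breastfeeding, with each mother counted once, would be sound. The text describes a trend of breastfeeding across months, which is not that layout.

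**Nothing decisive rests on it.** This also stands. The test is supplementary, and group-by-time terms and survival analyses are already planned.

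**Conclusion.** The concern holds as a minor point. With visits as the ordered levels, the test's independence assumption fails by design, and nothing in the plan corrects for it.

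The size depends on inputs the plan does not give. At visits 1, 3 and 6 with permanent stopping, the standard error is 17 to 98% too large. With six monthly visits and serial correlation of 0.3 to 0.7, it is 10 to 15% too small. Some combinations happen to land near 5%, but the plan gives no basis for relying on that.

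The practical loss is for modest declines in an arm where breastfeeding persists. These figures assume 84 mothers per arm, a within-arm test at two-sided 5% and visit month as the score. The primary 6-month comparison is unaffected.

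**What to change.** Replace the Cochran-Armitage test, for any and for exclusive breastfeeding, with a trend test that allows for repeated measures: a GEE logistic model with mother-clustered robust standard errors, or a mixed logistic model. Test the group-by-time contrast and, if wanted, the trend within each arm. Name the visits used in the 6-month and 12-month windows. Alternatively, delete the trend test and rely on the planned survival and group-by-time analyses. If a one-row-per-mother layout was meant, state it.

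The cost is a change to the SAP wording and standard code, with no new data or visits.
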